13.2 Collection of adverse event reports

AE data must be collected from time of first trial-related activity after the subject has signed the informed consent form (ICF) until subject's completion of the clinical trial (all trial periods including safety follow-up visit at Week 17, see [Section 7.3](#)).

AEs must be assessed by medically qualified personnel.

At all visits, the subject will be asked a non-leading question by the investigator about AEs, e.g.: "How have you felt since I saw you last?" No specific symptoms should be asked for. It is important that the investigator also observes the subject for any changes not reported by the subject and records these changes.

Any potential AE reported by the subjects during an exit interview must be collected by the interviewer on the Potential Adverse Event Collection Form. The interviewer must forward the completed form to the investigator within 24 hours of the interview. The investigator must evaluate if the potential AEs are indeed to be considered as AEs and whether they were already recorded in the eCRF and date and sign their evaluation within 24 hours of receipt of the form. Interviewer and investigator should confirm to each other receipt of the form by the investigator within those 24 hours. If the confirmed AEs were not recorded in the eCRF, or if the investigator is in doubt, they must record the AEs in the eCRF. If considered relevant, the investigator should follow up on the AEs with the subject no later than at the safety follow-up visit. If a potential AE qualifies as an SAE, the SAE must be reported within 24 hours of receipt by the site/investigator as described in [Section 13.4.1](#).

Principles for data recording in the eCRF are described in [Sections 11.4.1 to 11.4.4](#).

13.3 Reporting of adverse events

AEs reported by the subject or observed by the investigator must be recorded on the AE form of the eCRF and should be described in the following manner:

The AE term must be in precise English medical terminology (that is, not necessarily the exact words used by the subject). Whenever possible, a specific diagnosis should be stated (e.g. 'allergic contact dermatitis').

The duration of the AE must be reported by the start date and stop date of the event unless the event is ongoing. If the event is ongoing, it will be marked as ongoing. In addition, it will be recorded if the AE started prior to first administration of IMP.

AEs must be classified in terms of severity, causality, and outcome according to the definitions in [Appendix 2](#).

Action taken with IMP: any action taken with IMP as a consequence of the AE must be recorded in the eCRF (dose not changed, drug interrupted, drug withdrawn, not applicable, unknown).

Other action taken: any other action taken as a result of the AE must be recorded in the eCRF (none, concomitant medication, concurrent procedure).

It must be recorded in the eCRF if the AE led to permanent discontinuation of IMP and/or withdrawal from trial.

13.4 Reporting of serious adverse events

The criteria that define an AE as serious (that is, an SAE) are defined in [Appendix 1](#). SAE criteria are also listed on the SAE form.

13.4.1 Investigator reporting responsibilities

Any SAE must be reported to LEO Pharma on the (paper) SAE form within 24 hours of first knowledge. For timing of SAE reporting in Germany, see [Appendix 4](#). This report should contain amongst others an assessment of available information on seriousness, severity, causal relationship to the IMP or trial procedure, the action taken, the outcome to date, and a narrative description of the course of the event. For more details regarding reporting of any SAE, please see the guidance text on the SAE form.

By signing and dating the SAE form, the investigator acknowledges that he/she is aware of the SAE and has assessed the causal relationship of the IMP(s) and any of the other medications to the SAE.

The actual reporter, if not the investigator, should also sign and date the SAE form.

The completed SAE form must be faxed or scanned and e-mailed to Global Safety at LEO Pharma using the e-mail address or fax number below:

Global Safety at LEO Pharma

E-mail address: [contact].

[contact].

If relevant, the investigator will enclose other information with the SAE form, such as anonymized reports of diagnostic procedures, hospital records, autopsy reports, etc.

Additionally, Global Safety at LEO Pharma may request further information in order to fully assess the SAE. The investigator must forward such information to LEO Pharma upon request by fax or e-mail (see contact details above).

The investigator must notify the local IRB(s)/IEC(s) of SAEs, as required by current applicable legislation for the concerned country.

SAEs occurring after the completion of the clinical trial should not be routinely sought or recorded. However, such events should be reported to Global Safety at LEO Pharma (see contact details above) if the investigator becomes aware of them.

13.4.2 LEO Pharma reporting responsibilities

Global Safety at LEO Pharma is responsible for assessing whether an SAE is expected. The relevant reference safety information document for this clinical trial is the investigator's brochure edition 3.0 Section 7.2 and subsequent updates.

Global Safety at LEO Pharma will notify the regulatory authorities and concerned investigators of SAEs according to the current applicable legislation for the concerned countries.

The IRB(s)/IEC(s) will be notified of SAEs according to the current applicable legislation for the concerned countries.

For all non-US countries, the following reporting requirements apply: all SAEs which are assessed as causally related to the IMP(s) by either the investigator or LEO Pharma (33), and which are unexpected (suspected, unexpected serious adverse reactions [SUSARs]), are subject to expedited reporting to regulatory authorities, IEC(s) according to the current applicable legislation in the concerned countries. Investigators will be notified of the evolving safety profile of the IMP on an ongoing basis.

In US, the following reporting requirements apply: all SAEs which are assessed as causally related to the IMP(s) by LEO Pharma (60, 61) and which are unexpected (serious and unexpected suspected adverse reactions [IND safety report]) are subject to expedited reporting to regulatory authorities, IRB(s). Investigators will be notified of the evolving safety profile of the IMP on an ongoing basis.

13.5 Other events that require expedited reporting

13.5.1 Pregnancy

Any pregnancy occurring after first exposure to IMP and until the subject has completed the trial must be reported to LEO Pharma within 24 hours of first knowledge using the (paper) pregnancy form (part I). All pregnancies must be followed up until delivery or termination and outcome must be reported on the (paper) pregnancy form (part II) within 24 hours of first knowledge.

The completed pregnancy forms must be faxed or scanned and e-mailed to Global Safety at LEO Pharma. Contact details are given in Section 13.4.1.

Pregnant subjects must immediately discontinue IMP permanently and be withdrawn from the trial (Section 10.2 and Section 10.3).

13.6 Reporting of other events

13.6.1 Adverse events of special interest

The events listed in Panel 13 are considered AESIs in this trial and will require additional data to be recorded in the eCRF. LEO Pharma may request that the investigator forwards additional test results, as appropriate. An AESI may be serious or non-serious. Serious AESIs require expedited reporting via the SAE form as described in Section 13.4. AESIs will be reviewed by the DMC (Appendix 3H).

Panel 13: Adverse events of special interest

Adverse event of special interest	Rationale	Additional data to be recorded	Data collection method
Eczema herpeticum	Eczema herpeticum is a well-known severe skin infection in patients with AD which occurs in lesional skin. The additional information will be collected to better understand the pathogenic nature of the eczema.	Skin findings: 
 • Lesion type (papules, vesicles, crusts, eroded pits, other [if other, a specification should be provided]). • Disseminated / localized. • Location (face, scalp, back, chest, upper limb, lower limb, genitals). • Present in an area with visible eczema / no visible eczema / present in areas with and without eczema. • Monomorphic / polymorphic. • Confirmation of herpes simplex virus (PCR, viral culture, Tzanck test, other [if other, a specification should be provided], not confirmed). 	eCRF
Skin infection requiring systemic treatment	Patients with AD are predisposed to develop skin infections due to impaired skin barrier and modified cutaneous immune response. Bacterial and viral infections represent the most common complications of AD. The additional information will be collected to better understand the pathogenic nature and localization of the skin infection.	
 • Location (face, scalp, back, chest, upper limb, lower limb, genitals). • Outcome of pathogenic swab (positive [staphylococcus aureus, streptococcus, candida, other, if other, a specification should be provided], negative, not performed). 	eCRF

Adverse event of special interest	Rationale	Additional data to be recorded	Data collection method
Electrocardiogram CCI [REDACTED]	This AESI was defined based on data from the first-in-human trial with LEO 152020 (39)	
 • ECG (measured according to the schedule of trial procedures [Section 4]). • Severity of the CCI [REDACTED] (mild, moderate, severe, see QTcF severity criteria in Panel 14). • Symptoms believed to be related to the CCI [REDACTED] and duration of the symptoms. 	eCRF

Abbreviations: AD = atopic dermatitis; AESI = adverse event of special interest; ECG = electrocardiogram; eCRF = electronic case report form; PCR = polymerase chain reaction (test); CCI [REDACTED]

AESIs of electrocardiogram QT corrected interval prolonged

QTcF >450 ms (men) and QTcF >460 ms (women) are considered clinically relevant QT prolongations and must be reported as AEs. QTcF severity of the AE must be recorded in the eCRF (see Panel 14 for guidance). For guidance on handling events of QT prolongation, see Section 11.4.3.

Panel 14: Severity specifications for adverse event of electrocardiogram CCI [REDACTED]

Mild	Moderate	Severe
Men: 450 ms < average CCI [REDACTED] ≤ 480 ms Women: 460 ms < average CCI [REDACTED] ≤ 480 ms	480 ms < average CCI [REDACTED] ≤ 500 ms or 30 ms < increase in CCI [REDACTED] from baseline ≤ 60 ms	Average QTcF > 500 ms or Increase in QTcF from baseline > 60 ms

Abbreviations: CCI [REDACTED]

^a Modified from (62) in line with the CCI [REDACTED] guideline on clinical evaluation of CCI (34).

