^e The informed consent form must be signed prior to conducting any protocol-related assessments/procedures, including but not limited to screening evaluations and washout of disallowed medications. Screening evaluations may start later than the date when the informed consent form was signed.

^f At screening, the demographic data listed in Section 11.2.1 will be recorded. At baseline, only age will be recorded on the randomization form.

^g BSA affected by AD will be assessed as component A of SCORAD (Section 11.3.3).

^h If the results of the hepatitis B, C, HIV, and/or tuberculosis tests are inconclusive at screening, they may be repeated at an unscheduled visit, if necessary.

ⁱ At each visit between baseline and Week 14, the subject will self-administer the morning dose of IMP at the trial site under the supervision of the site staff.

^j Between visits from baseline to Week 16, the subject will self-administer the IMP at their home. The subject will take their last dose of IMP in the evening before the Week 16 visit.

^k ADSD, Nocturnal [REDACTED] Difficulty [REDACTED] Frequency of [REDACTED] During the Night, [REDACTED] and [REDACTED] will be completed in the eDiary daily.

^l Includes ADSD PGI-S, [REDACTED] PGI-S, Nocturnal [REDACTED] PGI-S, Difficulty [REDACTED] PGI-S, Frequency of [REDACTED] During the Night PGI-S, [REDACTED] PGI-S, and [REDACTED] PGI-S.

^m Includes ADSD PGI-C, [REDACTED] PGI-C, Nocturnal [REDACTED] PGI-C, Difficulty [REDACTED] PGI-C, Frequency of [REDACTED] During the Night PGI-C, [REDACTED] PGI-C, and [REDACTED] PGI-C.

ⁿ See Panel 3 for more information.

^o It will be at the discretion of the investigator if a urine sample should be sent to the central laboratory for further analysis.

^p Women of childbearing potential only.

^q Wristband actigraphy, skin biopsies, and exit interviews are optional components of the trial for subgroups of subjects. Participation in these components is not required for participation in the core part of the trial and the subject will be asked to provide additional consent.

^r At the indicated visits, subjects will be asked to bring the wristband actigraphy devices back to the site and the investigator or site staff will transfer data from the devices. Subjects will be asked to return the devices at Week 16 or at their last visit in the trial.

^s Skin biopsies should be taken from the locations described in Section 11.7.3.

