^t Exit interviews should be scheduled as described in Section 11.7.4.

Panel 3: Schedule of ECG measurements and PK blood samples in relation to fasting and administration of IMP

Week -5 (screening)	Week -1 (run-in)	Week 0 (baseline)	Week 1	Weeks 2, 6, 10, and 14	Weeks 4, 8, and 12	Week 16	Week 17 (safety follow-up)	Early termination	
NA	NA	Subject is fasted ^c					NA	NA	

 • 3 consecutive ECGs ^a • Laboratory assessments 	
 • 1 ECG ^b • Laboratory assessments 	
 • Pre-dose ECG ^d • Pre-dose PK ^e • Laboratory assessments 			
 • Pre-dose PK ^g • Laboratory assessments 	
 • 1 ECG ^b • 1 PK • Laboratory assessments 	
 • 1 ECG ^b • Laboratory assessments 	
 • 1 ECG ^b • 1 PK • Laboratory assessments 	
NA	NA	Administration of IMP Wait CCI and proceed with				Subject may break fast	NA	NA	
		
 • Post-dose ECG • Post-dose PK ^f 	
 • Post-dose ECG • Post-dose PK ^f 	
 • Post-dose ECG 	
 • Post-dose ECG • Post-dose PK ^f 				
NA	NA	Subject may break fast					NA	NA	NA
		
 • Japan: post-dose ECG (4 hours±15 min after dosing) ^h 	
 • Japan: post-dose ECG (4 hours±15 min after dosing) ^h 						

Abbreviations: ECG = electrocardiogram; IMP = investigational medicinal product; NA = not applicable, PK = pharmacokinetic(s).

If at any ECG measurement, the subject presents with a **CCI**, the ECG should be repeated. If the **CCI** is confirmed, a PK sample (if not already planned at the visit) must be taken close to the last ECG. See Section 11.4.3 for more information.

THIS DOCUMENT CONTAINS CONFIDENTIAL INFORMATION AND MUST NOT BE COPIED OR MADE AVAILABLE TO ANY THIRD PARTY WITHOUT THE PRIOR WRITTEN CONSENT OF THE LEO PHARMA GROUP

- ^a In line with exclusion criterion 13. Must be measured before any blood sample collected at the same visit.
- ^b Must be measured before any blood sample collected at the same visit.
- ^c The subject will be asked to come fasted to the trial site, i.e. arrive at the site minimum 2 hours after their last meal.

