11.4.3 Electrocardiography

ECGs must be measured according to the schedule of trial procedure and special attention should be paid to timing of measurements (see Section 4, Panel 2 and Panel 3, for more information). 12-lead resting digital ECGs will be recorded after the subject has been in supine position for at least 5 minutes.

At an unscheduled visit, it will be at the discretion of the investigator if an ECG should be measured.

The investigator must evaluate each ECG for immediate subject safety and date and sign their evaluation. In case of a suspected abnormal ECG, the investigator must take appropriate action, at their discretion.

All ECG data will be transferred to a central ECG service company for central evaluation. At the service company, a cardiologist will analyze and interpret the ECG data and provide ECG evaluation reports to the trial sites.

The investigator must review the ECG reports and evaluate all abnormal ECGs (clinically significant or not clinically significant). The investigator must document their review by signing the ECG reports at the trial site. The investigator is ultimately responsible for judging the clinical significance of any abnormal ECG. However, **CCI** >450 ms (men) and **CCI** >460 ms (women) are considered clinically relevant **CCI** and should therefore be reported as AEs as described in Section 13.6.1.

If a subject presents with a **severe CCI**, i.e. **CCI** >500 ms or an increase in **CCI** from baseline >60 ms, the ECG should be repeated. If the **CCI** or increase in **CCI** from baseline is confirmed:

- A PK sample (if not already planned at the visit) must be taken close to the last measured ECG.
- The subject must permanently be discontinued from IMP.

If the subject presents with a **moderate CCI**, i.e. 480 ms < **CCI** ≤500 ms or 30 ms < increase in **CCI** from baseline ≤60 ms, the ECG should be repeated. If the **CCI** or increase in **CCI** from baseline is confirmed:

- A PK sample (if not already planned at the visit) must be taken close to the last measured ECG.
- A post-dose ECG and post-dose PK sample must be taken as described in Panel 3 for Week 1 at every visit onwards and as long as the subject presents with the moderate QT prolongation.

If the subject returns to **CCI** ≤480 ms (mild **CCI** or normal **CCI** interval) and increase in **CCI** from baseline ≤30 ms, the ECG and PK monitoring schedule described in Section 4 should be followed again.

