11.6 Pharmacokinetic and pharmacodynamic assessments

11.6.1 Pharmacokinetic assessments

Blood samples for the measurement of LEO 152020 plasma concentration (C_{trough} and C_{max}) will be collected according to the schedule of trial procedures and special attention should be paid to timing of collection (see Section 4, Panel 2 and Panel 3, for more information).

Pre- and post-dose PK blood samples should be collected within 5-10 min after the pre- and post-dose ECGs, respectively (see also Section 11.4.3 for more information about timing for the ECG measurements).

Given the time window for post-dose ECG measurements (1 hour±15 min after dosing), the time window for a post-dose PK blood sample is CCI after dosing.

Instructions for collection, handling, and shipment of PK samples will be provided in a separate laboratory manual.

PK samples of subjects treated with LEO 152020 will be analyzed by an external laboratory using a validated bioanalytical method. The method used to analyze the samples will be described in a separate bioanalytical report appended to the CTR.

Reporting in eCRF

It will be recorded in the eCRF if PK blood samples were collected. If not, a reason should be provided.

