14.3.14.3 Electrocardiography

Absolute values and change in ECG parameters (CCI [REDACTED]) from baseline to each relevant visit will be summarized by treatment group as mean, SD, median, minimum and maximum values for the safety analysis set.

Subjects with abnormal clinically significant ECG parameters will be listed. Furthermore, a shift table showing the change in clinical assessments (normal, abnormal not clinically significant, abnormal clinically significant) for the ECG parameters from baseline to Week 16 will be provided.

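### No stated output counts subjects by arm above 480 or 500 ms or with QTcF rises >30 or >60 ms, and rises of >30–60 ms that stay at or below 450/460 ms may be missing from the AESI counts

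*Combined protocol and SAP*

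**What the plan says.** **Reporting trigger.** Section 13.6.1: "QTcF >450 ms (men) and QTcF >460 ms (women) are considered clinically relevant QT prolongations and must be reported as AEs". Section 11.4.3 gives the same two limits. Neither sentence mentions a rise from baseline.

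**Grading.** Panel 14 has three grades: mild (above 450/460 and up to 480 ms), moderate (above 480 and up to 500 ms, or a rise >30–60 ms) and severe (above 500 ms, or a rise >60 ms). The rise criteria stand alone.

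**Action.** Section 11.4.3 uses the same moderate and severe limits. A confirmed moderate finding leads to a PK sample, then post-dose ECG and PK "at every visit onwards and as long as the subject presents with the moderate QT prolongation". A confirmed severe finding stops IMP, as Section 10.2 also requires.

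**Data source.** Section 11.4.3: "All ECG data will be transferred to a central ECG service company for central evaluation".

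**Planned ECG analysis (14.3.14.3).** Values and changes at each relevant visit "will be summarized by treatment group as mean, SD, median, minimum and maximum values for the safety analysis set", a listing of clinically significant abnormal cases, and a shift table of the normal/abnormal clinical assessment "for the ECG parameters from baseline to Week 16 will be provided".

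**ECG timing.** Panel 3 ("Schedule of ECG measurements and PK blood samples in relation to fasting and administration of IMP") places post-dose ECGs at Weeks 0, 1, 2, 4, 6, 8, 10, 12 and 14. Section 11.6.1 gives the "time window for post-dose ECG measurements (1 hour±15 min after dosing". Week 16 has a single ECG and no dose at the site. Panel 2, footnote j: "The subject will take their last dose of IMP in the evening before the Week 16 visit".

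**Related output.** Section 14.3.14.1 tabulates AESIs by treatment group.

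**The concern.** The ECG event is one of three AESIs, and the protocol sets numerical limits for it. A safety reader choosing a phase 3 dose would want to know how many subjects in each arm crossed each limit at any time on treatment. The stated ECG outputs do not give that. The one by-arm categorical table compares baseline with a visit away from the post-dose window, and it uses investigator judgement instead of QTcF limits.

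The AESI table is the natural fallback, but its content depends on what sites report. If one investigator reports a +40 ms rise ending at 430 ms and another treats it only as a monitoring trigger, the AESI counts are incomplete and differ by site.

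**Working it through.** No sample-size or power figure is involved. The check compares the planned outputs with the pre-defined limits, then applies the two QTcF rules to example values. Some parameter names in 11.4.3, Panel 14 and 14.3.14.3 are blacked out. I take them to include QTcF, because the limits match those printed in 10.2 and 13.6.1.

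**Step 1: what each planned output can count by arm**

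| Output | >450/460 ms | >480 or >500 ms | Rise >30 or >60 ms |
|---|---|---|---|
| 14.3.14.3 by-visit summaries | no | no | no |
| 14.3.14.3 listing | individual cases only, if judged clinically significant | same | same |
| 14.3.14.3 shift table | no (clinical judgement, Week 16) | no | no |
| 14.3.14.1 AESI table | yes, if reported | no breakdown stated | no breakdown stated |

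The by-visit maximum settles the count only when it stays below the limit at every visit; the number of subjects is then zero for the scheduled ECGs. If the maximum rise exceeds 30 ms at two visits, that may be one subject or two.

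Section 14.3.14.1 also presents AEs by severity. Appendix 2 defines severity by clinical judgement, and the plan does not say that the separately recorded QTcF grade feeds that table. If it did, the moderate grade would still mix values above 480 ms with rises >30 ms, and the severe grade would mix values above 500 ms with rises >60 ms.

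**Step 2: the shift table's end point.** Panel 3 has post-dose ECGs at Weeks 0, 1, 2, 4, 6, 8, 10, 12 and 14, which is 9 visits. Week 16 is not among them, so the table's end point uses 0 of the 9.

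**Step 3: where the reporting trigger and Panel 14 part.** Let b be the baseline QTcF, r the rise and L the trigger (450 ms men, 460 ms women). A rise goes unmentioned by the must-report sentence when b + r ≤ L.

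- Rise >30 ms: possible when b < L − 30, that is b < 420 (men) or b < 430 (women).
- The whole >30–60 ms band stays at or below L when b ≤ L − 60, that is b ≤ 390 (men) or b ≤ 400 (women).
- Rise >60 ms: possible when b < L − 60, that is b < 390 (men) or b < 400 (women).

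Examples:

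- Man, 390 to 425 ms: 425 − 390 = +35, below 450. Moderate in Panel 14, not must-report.
- Woman, 400 to 455 ms: 455 − 400 = +55, below 460. Moderate, not must-report.
- Man, 385 to 450 ms: 450 − 385 = +65, not above 450. Severe and IMP stopped, yet outside the must-report sentence.

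The entry limits in 8.3 (300 to 450/460 ms) apply to the screening triplicate, whereas baseline is Visit 3 under 14.3.1. The documents do not say how many subjects have baselines in these ranges.

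**Step 4: what catches the severe tier.** A confirmed rise >60 ms stops IMP (10.2, 11.4.3). Appendix 1 counts the reason for an unplanned change in medication as an AE, and 14.3.14.1 tabulates AEs leading to discontinuation. The open part is therefore mainly the >30–60 ms tier.

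**The case against.** **Panel 14 may only grade events already reported.** Section 13.6.1 first sets the trigger, then asks for the grade with Panel 14 as guidance, and the panel's title refers to the severity of an adverse event. Separate thresholds for reporting and for monitoring are not in themselves a contradiction. This reading is reasonable, but the protocol never states it, and 11.4.3 uses the rise limits as free-standing definitions of moderate and severe prolongation. What stands is that the text is unsettled; a flat contradiction is not shown.

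**There is a catch-all.** Section 11.4.3 makes any new clinically significant or clinically relevant ECG finding after first dose an AE, and the investigator reviews every central report. That recovers some cases, but by individual judgement, which is the source of possible site differences.

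**Light ECG reporting may be deliberate.** The amendment history says ECG parameters were dropped as endpoints because a dedicated trial is planned, and Section 5.5 plans to explore exposure against ECG findings. This lowers the stakes. Section 12.2 still says that ECG endpoints will be used to assess the effect of treatment.

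**The table is SAP-level detail.** No separate SAP is supplied, and it could contain the table. The point concerns the protocol text only.

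**Stronger readings that a reader might infer.** One is that QT prolongation is not counted by arm at all; the AESI table counts reported events above 450/460 ms. Another is that ECGs are analysed only at Week 16; the continuous summaries cover each relevant visit. A third is that subjects are less safe or the arms are compared with bias; monitoring and stopping do not depend on the AESI label, and blinding makes differential reporting unlikely.

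**Conclusion.** The point holds as a minor one. The stated outputs give no by-arm count of subjects above 480 or 500 ms, or with rises >30 or >60 ms. The reporting sentences leave open whether a >30–60 ms rise ending at or below 450/460 ms is an AESI.

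The size of any under-count cannot be derived: neither the baseline QTcF distribution nor the expected rises are given in the readable text. I give no illustrative range, because it would rest wholly on assumed means, SDs and extremes. What can be stated exactly is that the shift table's end point uses none of the nine post-dose ECG visits, and that the reporting gap is possible at baselines below 420 ms (men) or 430 ms (women).

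The conclusion assumes that the blacked-out parameter is QTcF and that no SAP table already covers the counts. No efficacy result and no protection of subjects is affected.

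**What to change.** 1. Add to 14.3.14.3 a table by treatment group, from the central ECG data, of the number and percentage of subjects with any post-baseline QTcF >450/460, >480 and >500 ms and with any increase >30 and >60 ms. Include all post-dose and unscheduled ECGs. Name the Visit 3 pre-dose ECG as baseline, since Panel 3 has both a pre-dose and a post-dose ECG at that visit. If the SAP already has this table, a cross-reference is enough.

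2. Align the reporting sentence in 11.4.3 and 13.6.1 with Panel 14. Either make every confirmed rise graded moderate or severe a reportable AESI whatever the absolute value, or state that >30–60 ms rises at or below 450/460 ms are monitoring triggers only and rely on the new table to count them.

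Cost: one extra safety table from data already collected and one or two sentences. AESI counts may rise slightly under the first option.
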